Annex 1. Constant scale

Annex 2. DASH scale

Annex 3. TNM classification

Annex 4. Visual Analog Pain Scale

Annex 5. International Physical Activity Questionnaire

Annex 6. EORTC Questionnaire QLQ-BR23

Annex 7. Patient Information Sheet

Annex 8. Patient Informed Consent Sheet

GENERAL INFORMATION

Document date: 30th October 2021

Main researcher: [name]

Main researcher: [name]

Main researcher: [name]

Center where the study will be carried out: Lymphedema Unit of the Sanitary Management Area

Campo de Gibraltar Oeste.

Head of the Lymphedema Unit of the A.G.S. Campo de Gibraltar West: [name].

Clinical Research Ethics Committee: This study will be presented to the Research Committee

Provincial.

Contact: [name]

Contact Phones: [name] / [name]

Contact email: [contact]

ABSTRACT

Breast cancer is the most common malignant tumor in women, with more than a million new cases annually. One of the most frequent surgical and post-actinic sequelae and well known is postmastectomy lymphedema. The axillary web syndrome is another sequel that limits the functionality of the patient and delays the protocol times of application of treatments cancer, and in many cases this sequela is misdiagnosed. This surgical sequelusually disappears spontaneously after the third month of appearance, but this implies a long period of discomfort and limitations for the user, at the same time that it may delay the application of Radiotherapy within the indicated protocol deadlines (due to the need for a body posture with abduction and flexion of the affected upper limb for its application and with the lymphatic thrombus is impossible to get).

With the present quasi-experimental study, the investigator intend to show that the application of Kinesitherapy and stretching from the beginning of the appearance of the cord, in a controlled and scheduled way by the physiotherapist, it is possible to reduce the time in which the lymphatic thrombus is present, and therefore, recover functionality, mobility, reduce pain and be able to apply the patients' treatments within of the established deadlines. The investigator intend to apply this therapy in the intervention group and compare thrombus evolution times with the control group.

QUALIFICATION

Effects of a manual therapy program to reduce the evolution time of axillary web syndrome in women affected by breast cancer.

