- Record of daily performance of lymphedema prevention kinesitherapy since the operation (days per week / duration in minutes / day).
- Approximate time elapsed since breast cancer diagnosis: years. Date format dd / mm / yy will be included, if possible.
- Stage in which the cancer is found, according to the TNM scale.
- Body mass index.
- Creation of a scale to classify the type of lymphatic thrombus (based on its location, length, thickness, pain, functional limitation and whether it is palpable-visible or not).

Result Variables:

- Level of physical activity measured by the International Physical Activity Questionnaire.
- -Quality of life questionnaire EORTC QLQ-BR23

Employment and leisure Variables:

- Employment situation at the time of data collection: Four categories have been assessed: Active / Retired / Unemployed / Home worker.
- Sport practice: yes / no.
- Sport and frequency.

Description of the intervention

15 sessions of Assisted Passive Kinesitherapy are carried out by the physiotherapist. Five days a week, for three weeks. If it is previously referred, the treatment will be finished earlier (the patient must achieve the same ranges of motion and strength as the contralateral limb, together with the remission of pain).

The stretches applied during the sessions will be gentle and maintained, never exceeding a pain grade 5 VAS (moderate pain), once the tension of the cord is reached between 20-30 seconds. A special effort will be made to recover flexion and abduction of the shoulder, bringing the cord to a tolerable tension on the part of the patient.

Friction will be made on the axillary scar to dislodge underlying planes and the subcutaneous tissue of the muscle fascia.

The patient will be trained in active kinesitherapy to prevent lymphedema and activate lymphatic circulation. Also with hygienic-postural measures for the same purpose.

CONTROL GROUP

All the variables and data for each patients are recorded in their clinical history. Goniometric study will be performed of the affected upper limb (shoulder, elbow, wrist). Constant scale, Quick-Dash, the Visual Analog Pain Scale and the International Scale of Physical Activity will also be performed. This assessment will be carried out the patient arrives at our unit and on day 30, 60, 90.

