Barthel Scale: The Barthel index or Barthel scale is an instrument used by social and health professionals for the functional assessment of a patient and to monitor their evolution. In the case of Social Workers, they value the independence or dependence of the person in each of the activities of daily living (ADL), obtaining as a result the level of performance of the person and carrying out a rehabilitative / compensatory intervention and / or maintenance according to the results obtained. Promoting and / or maintaining the independence of the person.

The scale measures the ability of a person to perform 10 activities of daily life, which are considered basic, in this way a quantitative estimate of their degree of independence is obtained. 100 points is the highest score and the best result in the patient's functionality. 0 points is the worst result and shows the worst functional status.

These patients will be instructed in hygienic-postural care and active assisted auto-kinesitherapy to perform daily for 30 minutes. It will be assessed every 30 days (see exercise pictures).

These exercises are explained to the patient to be executed at home.

Exercise 1.- Codman Pendulum exercises.

Exercise 2.- Standing, Affected shoulder flex sliding palm of the hand on the wall up and down. Keep maximum flex during 15 seconds.

Exercise 3.- Seated, Affected shoulder flex. Seated on a wheeled chair, leaning elbow on a table. Shoulder flex sliding chair backwards and forwards.

Lymphedema prevention exercises. (please visit our YouTube channel "Unidad Linfedema Algeciras": https://www.youtube.com/channel/UC2usHZkrmgyDfEsKhBWKrmw

INTERVENTION GROUP

As well as the control group, all the variables and data for each patient will be collected in their medical history. Goniometric study of the affected upper limb will be performed too (shouder-elbow-wrist). Constan scale, Quick- DASH, Visual Scale will also be completed together with Analogue of Pain and the International Scale of Physical Activity. This exploration will also take place during the first session and on the 30th, 60th and 90th day.

These users will arrive at the first diagnosis of the thrombus in our unit,in order to receive manual therapy by the physical therapist. (see therapy pictures).

They will receive 15 sessions of manual therapy the physiotherapist, 5 days a week ,each session being approximately 40 minutes long.

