The session will begin with pendulum exercises of the shoulder to warm up the joint and give proprioceptive stimulation to the joint capsule.

[figure not shown]
The physiotherapist will perform passive stretches looking to tensioning the lymphatic cord, never exceeding grade 6 VAS pain chart. Mainly the affected shoulder will be treated and if the cord reaches the crease of the elbow or thumb, the extension (frase sin sentido general hay que volverla a escribir).

Scar massage will be done in the area where the lymphatic cord originates at the proximal level while maintaining the tolerable tension of the lymphatic cord (during the massage also pain grade 6VAS will be exceeded).

Patients with developed lymphedema will receive Decongestive Physical Therapy (PDT) on the treated limb once the 15 day treatment described for the study is finished. Therefore, PDT does not influence on obtained contaminated results. Those patients who do not suffer from lymphedema do not receive PDT.

Manual Therapy, Scar Massage and exercises for the Intervention Group:

Exercise 4.- The Physiotherapist rests the affected limb diagonal to regular movement only if pain due to stretching is moderate.

Exercise 5.- The Physiotherapist rests the limb in shoulder flex following elbow extension.

[figure not shown]
Exercise 6.- The Physiotherapist places the limb in abduction position while patient can tolerate discomfort.

Exercise 7.- In case the cord reaches the elbow, the Physiotherapist holds the elbow extension combined with supination of the limb. The shoulder will be kept in flexed position as long as pain is moderate to keep the tension of the cord.

Exercise 8.- If the thrombus reaches the first finger, the Physiotherapist will try to reach the ulnar deviation of the wrist together with the flexion of the thumb. The shoulder will be kept in a flexed position and the elbow in an extended supination position.

ANALYSIS OF RESULTS

A descriptive analysis of all the variables included in the study will be presented at the overall level and by type of treatment in the Axillary Web Syndrome. For the qualitative variables, the relative and absolute frequencies will be presented. In the case of quantitative variables, summary statistics will be presented (mean, median, mode, minimum and maximum).

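### Starting decongestive therapy after the session course does not keep it out of the results, because every scheduled follow-up assessment comes later still

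*Combined protocol and SAP*

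**What the plan says.** The rule on PDT stands under Intervention Group. Patients with lymphedema receive PDT on the treated limb "once the 15 day treatment described for the study is finished". From this the protocol concludes: "Therefore, PDT does not influence on obtained contaminated results". The wording is garbled, but the sentence is presented as following from the timing, and no other reason is given. The next sentence reads: "Those patients who do not suffer from lymphedema do not receive PDT".

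The course is described under Description of the intervention as 15 sessions, "Five days a week, for three weeks", with an early stop: "If it is previously referred, the treatment will be finished earlier". The Workplan gives 12 sessions, Monday to Friday.

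Assessments in the intervention group: "This exploration will also take place during the first session and on the 30th, 60th and 90th day". In the control group: "This assessment will be carried out the patient arrives at our unit and on day 30, 60, 90". They cover goniometry, Constant, Quick-DASH, pain VAS and the physical activity scale. Shoulder mobility, Constant and DASH are the main variables.

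The Control Group section does not mention PDT. The variable list under Valuation Criteria contains neither lymphedema status nor PDT receipt or dates, and Analysis of Results does not deal with PDT.

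**The concern.** PDT that starts after the sessions cannot mix with the sessions. To leave the results untouched it would have to start after the outcomes are measured, and the schedule does not ensure that.

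Patients who qualify for PDT can be enrolled. Recruitment is from a Lymphedema Unit, lymphedema is not an exclusion criterion, and the PDT rule itself expects such patients. PDT is given on the limb whose mobility and function are the main variables.

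Balance between groups cannot be assumed. The study is quasi-experimental and describes no random allocation. The PDT rule sits in the intervention section and is timed by a course that controls do not receive. The sentence on patients without lymphedema could be read as covering both groups, so unequal use is possible in either direction but is not shown.

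The Background does not allow a null effect of PDT to be taken for granted. It reports good results when manual lymphatic drainage is combined with physical therapy in axillary web syndrome, and the cited paper's title names shoulder function and pain. The documents do not say what PDT contains here, and a combined programme does not isolate one component, so this supports caution and nothing stronger.

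If PDT use or its effect differs between groups, part of any difference in mobility, function or pain would belong to PDT and not to the programme. General objective I is to explore the size of the programme's effect, and that is the quantity affected.

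**Working it through.** **Step 1. The stated course length.** 5 sessions a week × 3 weeks = 15 sessions, which agrees with Description of the intervention.

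**Step 2. Last day of the course.** Every weekday start is considered, weekends are skipped, attendance is full, and the first session is counted as day 1 or as day 0.

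| Reading | Source | First session = day 1 | First session = day 0 | Range |
|---|---|---|---|---|
| 15 weekday sessions | Description of the intervention | day 19 (Monday start) or 21 | day 18 or 20 | 18–21 |
| 15 calendar days | Intervention Group, PDT rule | day 15 | day 14 | 14–15 |
| 12 weekday sessions | Workplan | day 16, or 18 (Friday start) | day 15 or 17 | 15–18 |

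Overall the course ends on day 14 to 21, or sooner under the early-finish rule. The three statements of length must be reconciled, but the conclusion is the same under each.

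**Step 3. Days open to PDT before each visit** (visit day minus course end):

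- Day 30: 30 − 21 = 9 to 30 − 14 = 16
- Day 60: 60 − 21 = 39 to 60 − 14 = 46
- Day 90: 90 − 21 = 69 to 90 − 14 = 76, which is 69/90 = 77% to 76/90 = 84% of follow-up

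Three of three scheduled post-baseline visits fall after PDT may begin; none falls before. These are days available for PDT, not days of PDT received, because no start delay is stated. An early finish lengthens them; missed sessions that are made up shorten them.

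**Step 4. Would missed sessions change this?** With the first session as day 1, days 1–28 contain 20 weekdays, and days 29 and 30 repeat the weekdays of days 1 and 2. Day 30 is therefore the 22nd weekday for a Monday to Thursday start. For a Friday start, day 30 is a Saturday and the 22nd weekday comes after it. For the 15th session to fall on or after day 30, 22 − 15 = 7 sessions would have to be missed and made up.

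**Step 5. Size of the distortion.** Let p be the share receiving PDT before a visit and D the mean effect of PDT on the outcome, in the intervention (1) and control (0) groups. The group difference is shifted by

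p1 × D1 − p0 × D0.

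The documents give none of the four terms, so no size, sign or upper bound follows. The shift is zero if shares and effects are equal. The 20% lymphedema prevalence in the Background is for mastectomized women in general and has no time horizon; it may be too high or too low for this sample.

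**Step 6. Precision cost of leaving out patients with baseline lymphedema.** The stated total is 46. The excluded share q is not given, so 10–50% is assumed, with the same share removed from each group. Remaining n = 46 × (1 − q); standard error ratio = √(1/(1 − q)).

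| q | Remaining n | Standard error ratio | Increase |
|---|---|---|---|
| 10% | 41.4 (about 41) | 1.054 | 5% |
| 20% | 36.8 (about 37) | 1.118 | 12% |
| 30% | 32.2 (about 32) | 1.195 | 20% |
| 40% | 27.6 (about 28) | 1.291 | 29% |
| 50% | 23.0 (23) | 1.414 | 41% |

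**The case against.** The strongest reply accepts the calendar and says that little follows from it. No bias is shown: the number of patients with lymphedema, the delay before PDT and any difference in its use between groups are all unknown. The day counts measure opportunity, not exposure. Patients without lymphedema are unaffected at every visit, and a patient whose PDT starts after day 30 has a clean day-30 visit. The sentence is garbled and may mean only that PDT does not mix with the session course. All patient data go into the clinical history, and the early-finish rule implies some look at motion, strength and pain during the course. For a preliminary exploration, programme followed by usual care is a legitimate comparison.

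Much of this stands as a limit on the claim. The figures are upper limits on exposure under full attendance, and unequal use is a possibility only. In-course observations, including cord disappearance before the course ends (the Abstract hopes to "reduce the time in which the lymphatic thrombus is present"), would precede PDT.

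It does not rescue the statement. If only non-overlap was meant, the text should say so; as written it speaks of results. Unscheduled observations do not protect the scheduled outcomes, and a clinical history is no substitute for listed variables when no extraction is planned. Comparing programme plus later care is acceptable, but only if the plan says that this is the comparison.

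Two technical points also stand. Analysis of Results specifies only summaries for quantitative variables, so the standard-error figures apply to whatever between-group comparison of means is eventually made. An extra assessment at the end of the course would give one measurement before PDT, but it adds a visit and leaves days 30, 60 and 90 as they are; it is optional.

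**Conclusion.** The concern holds. The protocol infers that PDT has no influence on the results from timing alone, and the timing does not support it: the course ends on about day 14–21, and all three scheduled post-baseline assessments (days 30, 60 and 90) come later. This rests on the stated visit days, full weekday attendance and PDT being allowed once the course ends; it holds under each of the three course lengths given.

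What is established is an unsupported statement about a co-treatment that the plan does not record, not a demonstrated bias. The size and direction of any distortion are unknown, and it may be zero. The plan should be corrected, because in a non-randomised comparison this limits what can be attributed to the programme, and PDT data not collected prospectively may be hard to recover.

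**What to change.** 1. Delete the non-influence statement, or limit it to saying that PDT does not overlap with the study sessions.
2. In both groups, record lymphedema status at baseline and at each visit, and PDT receipt and start date.
3. Report PDT use by group and visit.
4. State that the comparison is the programme plus any later PDT against control care plus any PDT.
5. Add one sensitivity analysis in patients without lymphedema at baseline. Selection on a baseline characteristic avoids selecting on what happens after treatment. PDT for lymphedema that develops later remains in this analysis, and the report should say so.
6. Reconcile the Control Group and Intervention Group sections on PDT, and the three statements of course length. No clinical rule is proposed here.

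The cost is a few data fields per visit, one table and one small analysis. Over the assumed 10–50% share with baseline lymphedema, that analysis would have standard errors 5% to 41% larger than the full sample of 46. The plan also loses its claim that the results are uncontaminated by PDT.

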- 41. Bleicher RJ. Timing and Delays in Breast Cancer Evaluation and Treatment. Ann Surg Oncol. 2018 Oct;25(10):2829-2838. doi: 10.1245/s10434-018-6615-2. Epub 2018 Jul 2.
- 42.https://www.cancer.org/es/tratamiento/tratamientos-y-efectos-secundarios/tipos-de-tratamiento/q uimioterapia/como-la-quimioterapia-es-usada-para-tratar-el-cancer.html

OBJECTIVES

GENERAL OBJECTIVES

- I. Determine a preliminary exploration of the magnitude of the effect of a kinesitherapy and stretching intervention for the functional recovery of the upper limb, the recovery of the surgical scar and the improvement of the quality of life in women who have suffered from breast cancer.
- II. Create a scale to objectively classify the axillary thrombus (based on its clinical manifestations).

SPECIFIC OBJECTIVES for general objective I:

- Check the intervention of assisted passive kinesitherapy and stretching for the improvement of the range of joint mobility of the affected limb in the shortest possible time.
- Analyze the reduction of pain and increase of the degree of functionality of the ipsilateral upper limb in patients with AWS after the intervention.
- -Determine the impact of the physiotherapeutic intervention on the quality of life of a mastectomized woman with lymphatic thrombus.
- -Analyse the physiotherapeutic intervention reduction of the time on the evolution of the Superficial Lymphatic Thrombus and the application of Radiotherapy within the terms established in the oncological protocols.

SPECIFIC OBJECTIVES for general objective II:

- Create a scale to objectively classify the axillary thrombus (based on its clinical manifestations).

METHODOLOGY

TYPE OF STUDY

Quasi-experimental, prospective study.

STUDY POPULATION

The study sample is made up of patients undergoing surgery for Breast Cancer who attend the Lymphedema Unit of the A.G.S. Campo de Gibraltar Oeste presenting Lymphatic Thrombus after the operation, the recruitment period being from December 2021 to December 2023.

CALCULATION OF SAMPLE SIZE

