To calculate the sample size, the prevalence of axillary network syndrome (AWS) described in the scientific literature was taken into account. It affects 30%. The 2020 records for patients who attended the Lymphedema Unit of A.G.S. Campo de Gibraltar Oeste has also been included adding 83 new patients. With these figures, a random sample of 46 individuals in total would be enough to estimate, with a 95% confidence and a precision of +-5 percent units, a population percentage of 10%.

SELECTION CRITERIA

Patients who meet all the inclusion criteria and no exclusion criteria will be included in this study prospectively.

INCLUSION CRITERIA

- Patient over 18 years old.
- Mastectomized patients (either radical or conservative surgery).
- Patient with lymphatic thrombus in the upper limb ipsilateral to the surgical intervention.

EXCLUSION CRITERIA

- Significant psychological alterations that would prevent the retrieval of the information necessary for the investigation.
- Significant neurological alterations that would prevent the retrieval of the information necessary for the investigation.
- Patients in a situation of legal dispute that would affect their intervention in this study.
- Metastasis not treated with chemotherapy treatment.

WITHDRAWAL CRITERIA

- Withdrawal of informed consent from the patient.
- Administrative decision taken by the researchers, promoter or a regulatory authority.
- Mild adverse event.
- Serious, unexpected or clinically relevant adverse event.

VALUATION CRITERIA

Main Variables:

- Mobility of the affected shoulder, measured by goniometry.
- Functionality assessment using the Constant and DASH scale (29,30).

Secondary variables:

Sociodemographic and clinical-surgical variables

- Age
- Marital status: married or in a common-law relationship, widowed, divorced or separated, single.
- Level of completed studies: illiterate, primary studies, secondary studies, university studies.
- Type of residence: in an urban / rural area.

- Children: yes / no.
- Mother after 30 years old: yes /no.
- Smoker: yes /no.
- Type of cancer. Four categories have been assessed: ductal, infiltrating, in situ, Paget's.
- Number of lymph nodes removed.
- Type of surgery (radical-conservative).
- Breast reconstruction (yes / no).
- Radiotherapy (yes / no).
- Time from surgery to the appearance of the Lymphatic Thrombus in days.

Clinical Variables:

- Visual Analog Pain Scale.
- Goniometry of all joints of the affected upper limb.

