For all study objectives in which two qualitative variables are related, the non-parametric Chi-square test will be used and, if necessary, the Fisher test will be used (in cases where the absolute frequency of more than 20% of the levels is less than 5 observations). To quantify the possible predisposing factors, the relative risk measures (RR), Odds ratio (OR) and their associated confidence interval will be obtained; Likewise, the sensitivity or specificity will be presented if it is considered necessary.

All analyzes will be accompanied by graphic representations for greater detail. Missing values will be those that are not completed.

All analyzes will be carried out with free R software and the significance level for all hypothesis testing is determined at 0.05.

WORKPLAN

The study will be carried out according to the following schedule:

Development and approval of the Provincial CEIC

OCTOBER 2021

Beginning of the recruitment period and action on the intervention group

DECEMBER 2021

Drafting of results, discussion and conclusions of the project

DECEMBER 2023

According to the schedule set forth, the research project will be completed in a period of 24 months.

The researcher [name] will register the patients, whether they are in the control group or in the intervention group. The physiotherapy intervention will be applied during 12 sessions from Monday to Friday to the selected patients.

The researcher [name] will be in charge of comparing the results with a double-blind system and thus comparing the results of the control group with the intervention group. The researcher [name] will be the methodological advisor in this research.

[name], with the help of [name] and [name] will write the results, discussion and conclusions of the project.

DISSEMINATION AND DISSEMINATION PLAN

- 1. Publication in journals indexed in the Journal Citation Report (JCR), in the field of Oncology and Rehabilitation and Physical Medicine and Physiotherapy.
- 2. Dissemination of results in national and international Congresses of Oncology and Rehabilitation and Physical Medicine and Physiotherapy.
- 3. Dissemination to the public, press releases and explanatory brochures of the project.
- 4. Dissemination on the website of the A.G.S. Campo de Gibraltar West.

ETHICAL ASPECTS OF THE RESEARCH

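### For the quantitative main variables the plan names no SD, no between-group difference with confidence interval and no use of baseline, and thrombus evolution time has no defined duration variable or method

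*Combined protocol and SAP*

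**What the plan says.** Under Valuation criteria the main variables are shoulder mobility by goniometry and function by Constant and DASH. The Control group and Intervention group sections schedule these at first assessment and days 30, 60 and 90.

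Analysis of results describes all variables "at the overall level and by type of treatment in the Axillary Web Syndrome". For quantitative ones: "In the case of quantitative variables, summary statistics will be presented (mean, median, mode, minimum and maximum". The named test is for other data: "For all study objectives in which two qualitative variables are related, the non-parametric Chi-square test will be used", with Fisher as fallback. The one confidence interval is here: "To quantify the possible predisposing factors, the relative risk measures (RR), Odds ratio (OR) and their associated confidence interval will be obtained". A 0.05 level is set for all hypothesis tests. The Workplan assigns a researcher to compare the two groups' results, without naming a method.

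General objective I is to "Determine a preliminary exploration of the magnitude of the effect of a kinesitherapy and stretching intervention". Type of study is quasi-experimental, and no rule for entering either group is given.

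On evolution time, the Abstract intends to "compare thrombus evolution times with the control group", and a specific objective reads "Analyse the physiotherapeutic intervention reduction of the time on the evolution of the Superficial Lymphatic Thrombus". The only thrombus time among the listed variables is "Time from surgery to the appearance of the Lymphatic Thrombus in days".

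**The concern.** Sizing an effect takes a difference between groups and a statement of its uncertainty. The listed summaries give the first only by subtraction and the second not at all: without an SD a reader cannot build an interval, and minimum and maximum are a poor guide to spread. Baseline would appear in the tables, so a different starting point might be visible. How much of a day-30, 60 or 90 difference it explains would not be. This matters more here than in a randomised trial, because nothing in the design makes the groups alike at entry.

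Evolution time is a headline aim. The interval from surgery to cord appearance ends before therapy starts, so it cannot show an effect of therapy.

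**Working it through.** **Inputs.** The total of 46 comes from Calculation of sample size. The split (23/23), complete data, equal SDs (set to 1), the baseline-outcome correlation r = 0.3 to 0.7 and any baseline imbalance are assumptions; the documents give none of them.

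**The plan's own figure.** n = N·z²·p·q / (d²(N−1) + z²·p·q), with N = 83, p = 0.10, d = 0.05. With z = 1.645 this is 45.1, rounded up to 46; with z = 1.96 it is 52.1, i.e. 53. Either way it sizes one percentage and supplies no SD or target difference for the main variables. I use 46 only as the number analysed.

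**1. What is lost without an SD.** CI = difference ± 2.015 × SD × √(2/23). For an assumed mean difference of 15 points:
- SD 10: 9.1 to 20.9
- SD 20: 3.1 to 26.9
- SD 30: −2.8 to 32.8

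The same two means fit all three intervals.

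**2. Precision with and without baseline.** Half-widths in SD units:
- Unadjusted: 2.015 × √(2/23) = 0.594.
- Adjusted, balanced baselines: 2.017 × √(1−r²) × √(2/23) = 0.567, 0.515, 0.425 for r = 0.3, 0.5, 0.7.
- Adjusted, true imbalance D = 0.5 SD: the last factor becomes about √(2/23 + (D² + 2/23)/42), giving 0.59, 0.54, 0.44.
- Change score: 2.015 × √(2(1−r)) × √(2/23) = 0.703, 0.594, 0.460.

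At r = 0.3 with a 0.5 SD imbalance, adjustment gains almost no precision.

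**3. Bias.** Suppose no therapy effect, a systematic imbalance of 0.2 to 0.5 SD and a two-sided 0.05 test.

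(a) The imbalance acts only through the recorded baseline (follow-up shift = imbalance × r):
- Unadjusted: bias 0.2 × 0.3 = 0.06 to 0.5 × 0.7 = 0.35 SD; false positives about 5.5% to 21%.
- ANCOVA: about 5%.
- Change score: 6% to 17%. At r = 0.3 and imbalance 0.5 it gives about 17%, against 8% unadjusted.

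(b) The difference persists in full at follow-up:
- Unadjusted: bias 0.2 to 0.5 SD; false positives 10% to 38%.
- ANCOVA: bias = imbalance × (1−r), 0.06 to 0.35 SD; false positives 6% to 21%.
- Change score: about 5%.

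Neither method is safe under both assumptions. In both, ANCOVA does no worse than the unadjusted comparison.

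**4. Evolution time.** Setting the sections side by side:
- The Control group section defines cord presence as a nominal variable with an examination method.
- The clinical variables include a thrombus scale that covers, among other features, whether the cord can be felt or seen.
- Neither is named among the day 30, 60 and 90 assessments of either group.
- No start, end or duration is defined, and no time method is given.
- The Abstract puts spontaneous disappearance after the third month from appearance; the Background puts it within three months. Visits 30 days apart place resolution only within a 30-day window. Cords still present at day 90 are right-censored, and these two statements imply different amounts of that.

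**The case against.** The strongest reply is that the plan is not as empty as it looks. A group comparison is promised and a significance level set, so it would be wrong to infer that the plan commits to an unadjusted analysis, or to none: the method is unspecified. That stands, but silence still leaves variable, visit and method to be chosen after the data are seen.

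A reader might also infer that evolution time cannot be addressed at all. The documents do not support that. Cord presence is defined, a thrombus scale is listed, and all variables go into the clinical history; if recorded at each visit, cord presence by group could be compared by Chi-square or Fisher. What is missing is narrower: a stated visit schedule for the cord, a duration variable and a time method.

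A third reply is that the study is exploratory, and that ANCOVA with a change-score check is partly preference. In part this stands. The SD and a difference with its interval are the minimum, and the change-score check is optional. But calling the work preliminary does not remove the need for precision, since estimation is the stated purpose.

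Finally, the sizes rest on assumptions. Patients may be withdrawn even for a mild adverse event, so complete data is optimistic. Whether the groups will differ at baseline is unknown, and nothing here shows that they will.

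**Conclusion.** The point holds. As written, the plan cannot deliver the size and precision of effect that general objective I seeks for its main variables, and it leaves the recorded baseline out of any comparison. That conclusion comes from the text alone and does not depend on the figures.

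The figures give the scale under the stated assumptions. Unadjusted precision of about 0.59 SD is coarse. Adjustment improves it to between 0.57 and 0.42 SD when baselines are balanced, but only to between 0.59 and 0.44 SD with a 0.5 SD imbalance. At low correlation the reason to adjust is bias. It would go too far to say that adjustment removes bias: it does so in scenario (a), only in part in (b), and not for unrecorded differences.

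For evolution time the gap is one of definition, visit timing and method. It should be closed before analysis, and the recording part while visits can still capture it.

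**What to change.** In Analysis of results:
- Report n and SD by group and visit for each quantitative variable.
- For each main variable, give the baseline-adjusted between-group difference with 95% CI at days 30, 60 and 90, by ANCOVA or a mixed model using the first-assessment value.
- Say which goniometric measure and which DASH form is analysed: the visit schedules name Quick-DASH, while the description is of 30 items.
- Treat the intervals as exploratory unless one variable and visit is named primary. Three variables at three visits give at least nine; nine independent 0.05 tests would carry 1 − 0.95⁹ = 37% familywise error.
- Optionally add a change-score analysis as a sensitivity check.
- State how patients enter each group, and that adjustment does not remove unrecorded differences.

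For evolution time:
- Define start and end.
- Record cord presence by the examination already described, at the existing visits in both groups.
- Compare groups with a method that handles interval censoring and right censoring at day 90, with a 95% CI.
- Reconcile the Abstract and Background on natural course, since they determine how much censoring to expect.

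Cost: SAP wording, a modest analysis in R of values already collected, one degree of freedom for baseline, and one recorded item at existing visits. The change-score check has its own price: it is less precise than ANCOVA and, as shown above, can do worse than the unadjusted comparison. If many cords persist beyond day 90, the visit-based comparison will be less informative than the low cost suggests.
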